The dosing regimen of the Phase II trial will consist of 6 separate intrathecal doses, spaced 2 months apart. This extended dosing is designed to achieve optimal results based on the dosing experience of the phase I trial and the 6-patient pilot study. The outcomes of the 6-patient pilot study suggested that multiple dosing of up to 5 separate doses was safe and well-tolerated [3]. This pilot study informed dosing for the Phase I clinical trial, which consisted of 3 doses spaced 3 months apart. The three doses were extremely well tolerated. Notably, we observed transient improvements in some patients that were not sustained after the third dose, suggesting that the peak response had not yet been reached. We propose doubling the amount of treatments and increasing the frequency to every 2 months as a way of reaching a plateau of response in patients. The peak of response needs to be established in the Phase II study.

2. Clinical Study Objectives:

2.1 Primary objective:

- To determine efficacy of multiple (6) intrathecal administrations of autologous MSC-NPs compared to placebo through assessment of disability outcomes.

2.2 Secondary objectives:

- To determine continued safety and tolerability of multiple intrathecal injections of MSC-NPs in patients with MS.

3. Study Design:

The study is a Phase II, double-blind, placebo-controlled, randomized, parallel study design with a compassionate crossover element. The IT-MSC-NP treatments and all clinical assessments will take place at a single center (Tisch MSRCNY). Both the patient and the examining neurologist will be blinded to the treatment. The treating clinician ([name], principal investigator) and the cell manufacturing coordinator ([name], co-PI) will not be blinded. Study subjects will be assigned to blocks stratified by baseline EDSS score (3.0-4.0, 4.5-5.5, 6.0, and 6.5) and disease subtype (SPMS or PPMS). The total number of subjects in each block is shown below. Subjects in each block will be randomized into placebo or treatment group in order of date of consent based on randomization scheme designated by [name]

[figure not shown]
[name] (Professor of Healthcare Policy & Research and Professor of Epidemiology in Medicine at Weill Cornell Medicine). In the second year, treated subjects will cross over to the placebo group and placebo subjects will cross over to the treated group. Study subjects are randomized in an equal fashion to study treatment and placebo at initial randomization.

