- Details regarding treatment/placebo procedures detailed in section 5.2.2 above
- Treatment visits will be conducted by the treating neurologist, [name]
- Duration of treatment visits will last approximately 5 hours
- Study subjects will be instructed to stay in bed and limit any physical activity for the 24 hours following each procedure.
- CSF for biomarker analysis discussed in 5.2.2
- Blood draw for serum and plasma biomarker analysis
- Vital Signs
- EDSS and MSFC (Month 20 Only). Follow-up by phone will occur 48 hours, 1 week, and 1 month after each treatment visit. The purpose of the follow-up phone call is safety assessment and to document any adverse events. Calls will be made either by the clinical trial manager, the clinical research assistants, or the adverse event physician. Assessment will include the following:
- Headache pain scale

Outcome assessments II (Month 27):

- The purpose of outcome assessment II visit is to evaluate effects of the treatment group in year 2 compared to the baseline visit at the beginning of year 2. In addition, these assessments will be used to evaluate any sustained effects of the treatment in year 1.
- The following exams will be conducted 3 months following the 12th treatment visit (\pm 1 week) by the study subject's examining neurologist and study coordinator
- Vital signs
- Physical exam
- Neurological exam
- Headache pain scale
- EDSS
- MSFC
- 6 Minute Walk Test
- 12 Item MS Walking Scale
- Bladder Survey
- Urinalysis and Culture to screen for UTI
- Lumbar Puncture with CSF Aspiration for biomarker analysis
- Blood draw for serum and plasma biomarker analysis
- The following exams will be scheduled to occur 3 months following the 12th treatment visit (\pm 1 week)
- MRI (brain, C and T spine) \pm Gadolinium enhancement
- Urodynamic testing of bladder compliance (ability of bladder to fill without accompanying rise in bladder pressure)

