6.4 Schedule of activities (Study Table)

| Tests and Assessments | Pre-treatment Phase | | | Treatment Phase, year 1 ² | | Safety FU | Outcome assessments I ³ | Treatment Phase, year 2 ² | | Safety FU | Outcome assessments II ² | Final FU ³ |
|--|--|-------------------------------|----------------------------|---|---|---|------------------------------------|---|---|--|-------------------------------------|------------------------------------|
| | Screening Visit Month -4 (Within 4 months prior to treatment phase) | Bone marrow visit Month -3 | Baseline visit Month -1 | Treatment group Months 0, 2, 4, 6, 8, 10 | Placebo group Months 0, 2, 4, 6, 8, 10 | FU by phone 48 hrs and 1 week after each treatment or placebo | All groups Month 13 | Treatment group (crossover from placebo) Months 14, 16, 18, 20, 22, 24 | Placebo group (crossover from treatment) Months 14, 16, 18, 20, 22, 24 | Follow-up by phone 48 hrs and 1 week after each treatment or placebo | All groups Month 27 | End of study follow-up Month 36 |
| ICF | X | | | | | | | | | | | |
| Serum and Plasma Biomarker Analysis Blood draw | | | | X | X | | | X | X | | | X |
| Screening Blood Draw ⁴ | X | | | | | | | | | | | |
| Bone marrow aspiration | | X | | | | | | | | | | |
| LP Procedure | | | | X | X | | | X | X | | | X |
| CSF aspiration for biomarker analysis | | | | X | X | | | X | X | | | X |
| Vital signs | X | X | X ⁵ | X | X | | X | X | X | | X | X |
| Physical exam | X | | X ⁵ | | | | X | | | | X | X |
| Neurol. exam | X | | X ⁵ | | | | X | | | | X | X |
| Headache pain scale | | X | | | X (12 total) | X | | | X (12 total) | X | X | |
| EDSS | X | | X ⁵ | X ⁶ | X ⁶ | | X | X' | X' | | X | X |
| MSFC (T25FW, 9HPT, PASAT) | | | X | X ⁶ | X ⁶ | | X | X ⁷ | X ⁷ | | X | X |
| 6 Minute Walk Test (6MW) | | | X | | | | X | | | | X | X |
| UD | | | X | | | | X | | | | X | |
| Brain, Cervical, and Thoracic MRI ±Gd | | | X | | | | X | | | | X | X |
| Twelve Item MS Walking Scale | | | X | | | | X | | | | X | X |
| Infectious disease test | X | | | | | | | | | | | |
| Pregnancy test (females) | X | | | | | | | | | | | |
| Drug & Nicotine Urine Testing | X ⁵ | | | | | | | | | | | |
| Urinalysis & Culture | | | X | | | | X | | | | X | |
| Bladder Survey | | | X | | | | X | | | | X | |
| Infectious Disease Questionnaire | X | | | | | | | | | | | |

¹Screening Blood Draw will include CBC with differential, ESR, Comprehensive Metabolic Panel, PT/PTT, and Thyroid Function Tests

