### 1.2 Study Design

The study is a Phase II, double-blind, placebo-controlled, randomized, parallel group design with a compassionate crossover element. The IT-MSC-NP treatments and all clinical assessments take place at a single center (Tisch MSRCNY). Both the patient and the examining neurologist are blinded to the treatment. The treating clinician ([name], principal investigator) and the cell manufacturing coordinator ([name], co-PI) are not blinded. The total study duration is 3 years upon enrollment. Each subject will initially attend 1 screening visit, 1 visit for bone marrow extraction, and 1 baseline visit. In the first year, each subject will receive 6 intrathecal injections of MSC-NPs or placebo spaced 2 months apart, followed by an outcome assessment visit 3 months after the 6th treatment. In the second year, subjects will cross-over into the opposite group, and will receive 6 intrathecal injections of placebo or MSC-NPs spaced 2 months apart, followed by an outcome assessment visit 3 months after the 12th treatment. There is an additional follow-up visit at the end of year 3.

**Study Name:** Autologous, Bone Marrow-Derived Mesenchymal Stem Cell-Derived Neural Progenitor Cells, Expanded Ex Vivo; Administered Intrathecally (Phase II Trial)

**Principal Investigator:** [name]

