### **4 STATISTICAL ANALYSIS OF THE PRIMARY AND SECONDARY STUDY OBJECTIVES**

#### **4.1 Analysis of the Primary Study Objective**

##### Primary Outcome:

The primary analysis will include all subjects meeting inclusion and exclusion criteria and who have completed a year of treatment/placebo and the 3 month post-treatment assessment. EDSS Plus composite score from 3 month post-treatment assessment will be compared to baseline.

Descriptive statistics will be calculated for patients at baseline for the entire cohort as well as by treatment status. Treatment and placebo group patients will be compared on continuous and discrete baseline characteristics to assess randomization.

The EDSS-Plus scale will be used as our primary endpoint with improvement on one or more of the 3 components (EDSS, T25FW and 9HPT). Improvement is defined as  $\geq 1$  point decrease from baseline EDSS if EDSS at entry is  $\leq 5.5$ , and a  $\geq 0.5$  point decrease from baseline EDSS if EDSS at entry is  $\geq 6.0$ ,  $\geq 20\%$  positive change in T25FW, and/or  $\geq 20\%$  positive change in 9HPT confirmed. The primary endpoint of improvement on one or more of the 3 EDSS-Plus categories between treatment and placebo groups will be assessed bi-varately using the chi-square or Fisher's exact test, as appropriate, at year 1, 2, and 3 of the study. Adjusted odds ratio (95%CI) between treatment and placebo groups at each time point will be estimated through mixed effect logistic regression with fixed effect of time, treatment, relevant covariates, and random effect of patients. The three components of the EDSS-Plus composite score will also be assessed individually at all time points. A longitudinal linear mixed-effect model will be used to assess longitudinal change (percentage change in mean time) from baseline to 3 years for T25FW and 9HPT, with random intercepts for patients and taking into account treatment status (treatment vs placebo), disease subtype (SPMS vs PPMS) and time-progression status interaction.

**Study Name:** Autologous, Bone Marrow-Derived Mesenchymal Stem Cell-Derived Neural Progenitor Cells, Expanded Ex Vivo; Administered Intrathecally (Phase II Trial)

**Principal Investigator:** [name]

Under parallel design, we will compare the outcomes of interest between the two study treatments, with outcomes at 1 year as the primary time point, secondary analyses will evaluate outcomes at years 2 and 3.

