## 4.2 Analysis of the Secondary Study Objective

### Safety Analysis

All observed or volunteered adverse events (serious or non-serious) and abnormal test findings, regardless of study group or suspected causal relationship to the study drug(s) will be recorded in the subjects' case histories and submitted for yearly reporting to the DSMB and FDA. For safety analysis, the following will be tabulated:

- Incidence of Adverse Events
- Relationship pf Adverse Events to Investigational Product

**Study Name:** Autologous, Bone Marrow-Derived Mesenchymal Stem Cell-Derived Neural Progenitor Cells, Expanded Ex Vivo; Administered Intrathecally (Phase II Trial)

**Principal Investigator:** [name]

- Severity of Adverse Event
- Serious Adverse Events
- Adverse Events Leading to Treatment Discontinuation
- Death
- Adverse Events of Special Interest

Summary descriptive statistics will be reported for each adverse event. For continuous outcome, mean(sd)/median(IQR) for whole sample and each group will be reported along with p-values from two-sample two-sided t-test or Wilcoxon rank-sum test as appropriate. For binary outcomes, number (%) of events will be reported along with p-values from Chi-squared test or Fisher's exact test as appropriate. Linear or logistic regression will be applied to estimate the treatment effect on each safety outcome. Analyses will be performed at the end of each of the three years.

All analyses will be performed in SAS Version 9.4 (SAS Institute Inc., Cary, NC) or R version 4.0.3 (2020-10-10).

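### SAP 4.2 plans a safety treatment effect at the end of all three years, but after the Month 14 crossover a year-3 test, or a cumulative year-2 test by randomised arm, no longer compares cells with placebo

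*SAP*

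**What the plan says.** Safety and tolerability is the stated secondary objective (Protocol 2.2, SAP 1.1). SAP 4.2 gives the analysis. On binary events: "For binary outcomes, number (%) of events will be reported along with p-values from Chi-squared test" or Fisher's exact test. On modelling: "Linear or logistic regression will be applied to estimate the treatment effect on each safety outcome". On timing: "Analyses will be performed at the end of each of the three years".

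Both documents switch both arms. Protocol section 3: "In the second year, treated subjects will cross over to the placebo group and placebo subjects will cross over to the treated group". SAP 1.2: "In the second year, subjects will cross-over into the opposite group". Protocol 6.2 places the year-1 procedures at Months 0 to 10 and the year-2 procedures at Months 14 to 24.

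SAP 4.2 does not say whether a group after Month 14 is the randomised arm or the current treatment, whether counts in years 2 and 3 are per year or cumulative, or how carry-over is handled. Elsewhere the wording leans towards current treatment: the Month 27 visit is to "evaluate effects of the treatment group in year 2", and a year-2 column of the schedule in Protocol 6.4 is headed "Treatment group (crossover from placebo". SAP 4.1, on efficacy, is mixed: "Under parallel design, we will compare the outcomes of interest between the two study treatments". That sentence goes on to make year 1 the main time point and years 2 and 3 secondary.

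On the start of the safety window, Protocol 9.4 codes and summarises adverse events from the first lumbar puncture onward, while SAP 4.2 gives no start date. Marrow aspiration takes place about three months before the first treatment (Protocol 6.2).

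**The concern.** A treatment effect needs two groups that differ in treatment. That holds in year 1. It does not hold for completers in year 3, nor for a two-year cumulative count by randomised arm, yet the SAP commits to the same tests and regressions at every yearly analysis. A null result from either comparison could be read as reassurance about an intrathecal cell product when the comparison could not have shown a cell-related excess. Even a year-2 comparison by current treatment has a weakness that the protocol itself anticipates, since Protocol 6.2 uses the Month 27 visit to look for lasting effects of year-1 treatment. If benefits can last, so can harms, and in the cell-first arm they would fall in the placebo column.

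**Working it through.** The documents give no adverse-event rates and no design figure for safety. The only power calculation (Protocol 9.2, SAP 1.5) concerns the efficacy endpoint and does not bear on this point, so there is no plan figure to reproduce. Dates and counts below come from the documents; all event risks are assumptions.

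**Inputs.** Procedures at Months 0 to 10 and 14 to 24, final visit at Month 36 (Protocol 6.2, 6.3); six MSC-NP and six placebo procedures per subject (Protocol summary table); 25 subjects per arm enrolled, 20% attrition expected (Protocol 9.2).

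**Step 1. Exposure at each analysis, subjects completing both periods.**

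| Analysis | Cell-first arm | Placebo-first arm | What a group comparison can show |
|---|---|---|---|
| End of year 1 | 6 cell | 6 placebo | Cells versus placebo |
| End of year 2 | 6 cell, then 6 placebo | 6 placebo, then 6 cell | Cells versus placebo only within year 2 and by current treatment |
| End of year 3 | 6 cell + 6 placebo | 6 placebo + 6 cell | Order and time since cells |

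Time since the last MSC-NP dose at Month 36: 36 − 10 = 26 months (cell-first) and 36 − 24 = 12 months (placebo-first). No study treatment is scheduled after Month 24, so grouping by current treatment is not available in year 3. This step needs no assumed rate.

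**Step 2. Cumulative to the end of year 2, by randomised arm.** Let the yearly risk be pT on cells and pC on placebo, with no carry-over, period effect or dropout. Either sequence gives 1 − (1 − pT)(1 − pC):

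- 30% and 10%: 1 − 0.70 × 0.90 = 37% in both arms; the year-1 difference of 20 points becomes 0.
- 20% and 5%: 1 − 0.80 × 0.95 = 24% in both arms; 15 points becomes 0.
- 60% and 20%: 1 − 0.40 × 0.80 = 68% in both arms; 40 points becomes 0.

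The cancellation is not exact if subjects leave. If a fraction d of each arm leaves after year 1 and before Month 14, the 30%/10% case gives (1 − d) × 0.37 + d × 0.30 against (1 − d) × 0.37 + d × 0.10. For d = 0.10 this is 36.3% against 34.3%; for d = 0.20 it is 35.6% against 31.6%. The difference is 2 or 4 points, against 20 in year 1. Carry-over also leaves a remainder: with an extra delayed risk of 10% in the cell-first arm, 1 − 0.70 × 0.90 × 0.90 = 43.3% against 37%, or 6.3 points.

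**Step 3. Year 2 only, by current treatment.** At 30%/10% without carry-over the contrast is 0.30 − 0.10 = +20 points, so it is intact. With an extra delayed risk c in the cell-first arm, the placebo column becomes 1 − 0.90 × (1 − c):

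| c | Placebo column | Contrast |
|---|---|---|
| 5% | 14.5% | 15.5 points |
| 10% | 19% | 11 points |
| 20% | 28% | 2 points |

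**Step 4. Follow-up after first MSC-NP exposure.** 36 − 0 = 36 months against 36 − 14 = 22 months. With 25 per arm and no attrition, 25 × 36/12 = 75 and 25 × 22/12 = 45.8 person-years. This does not measure the defect; it is why a post-exposure table should use rates.

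**The case against.** The strongest reply is that current treatment is the natural meaning of group in year 2. On that reading the second year is a concurrent cell-versus-placebo contrast, and SAP 4.1 already makes year 1 the main time point, though only for efficacy. The Phase I events described in Protocol 1.2 were short-lived (headache up to 48 hours, fever over within 24 hours), so carry-over of the expected events should be small, and the 20% case in Step 3 is extreme. No stopping or success rule is tied to these p-values. All of this stands. It limits the year-2 problem to a cumulative count by arm and to delayed events; it does not help year 3.

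Two stronger readings are tempting. One is that the year-2 safety effect will come out with the wrong sign. At 30%/10% a year-2-only comparison by randomised arm would indeed give 0.10 − 0.30 = −20 points, but that takes the less natural reading of group, and the parallel-design sentence in SAP 4.1 is weak support for it because it also speaks of comparing the two treatments.

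The other is that harms of marrow aspiration go unrecorded or untabulated. The documents do not support that. Protocol 8.2.2 records all adverse events and provides a hotline, 8.2.1 asks about events at every study visit (which includes the baseline visit after aspiration), the DSMB reviews all enrolled subjects (9.5), and the SAP 4.2 tabulations have no start date.

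**Conclusion.** The point holds, with high confidence for year 3. A year-3 treatment-effect test among completers does not compare cells with placebo, whatever the event rates. A cumulative year-2 test by randomised arm removes the effect entirely without carry-over or dropout, and leaves 2 to 4 of 20 points with 10% to 20% leaving between the periods; these sizes rest on assumed risks. A year-2 test by current treatment is usable but open to carry-over, and the SAP does not specify it. The year-1 comparison is unaffected by the crossover, although Protocol 9.4 does not define its analysis population. This should be fixed before the post-crossover analyses; it does not undermine the trial.

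The start date of the adverse-event window is a minor harmonisation gap. It affects both arms alike, and some subjects may use marrow harvested earlier under another protocol.

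**What to change.** In SAP 4.2:

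- Limit between-group safety p-values and regressions to events from the first lumbar puncture to the Month 14 procedure, in all subjects with at least one lumbar puncture. For subjects who never have that procedure, state an equivalent cut-off, for example the scheduled Month 14 date, or last contact if earlier.
- Plan no year-3 treatment-effect test.
- Report later events descriptively by sequence and period, showing subjects who never crossed over separately, and report events after first MSC-NP exposure per person-year.
- If a year-2 contrast is kept, prespecify it as current treatment, with events from the Month 14 procedure to Month 27 only, labelled as open to carry-over.

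As a minor change, align Protocol 9.4 with SAP 4.2 so that events after a marrow aspiration done under this protocol are tabulated, including in subjects who never reach a lumbar puncture, and name the analysis sets. Protocol 5.1.1 and 8.4 replace discontinued subjects while 13.1 does not; these statements must be reconciled because they affect the denominators.

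The cost is a few sentences and two or three tables, with no new visits. Formal post-crossover safety tests are given up, apart from the year-2 contrast if it is kept.
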